4.1.5 Analysis of laboratory and functional tests results

A between group comparison of the vital signs changes (systolic blood pressure, diastolic blood pressure, breathing rate, heart rate, body temperature) revealed at every visit (Visits 1, 2, 3) as well as laboratory results and ECG changes incidence obtained at Visit 1 and Visits 2–3 is envisaged. In addition, significance of the changes will be evaluated for all repeatedly measured parameters.

The following laboratory parameters will be reviewed:

- Hematology
 - o Hemoglobin
 - o RBC
 - o ESR
 - o WBC
 - o Neutrophils
 - Juvenile
 - Stab
 - Segmented
 - o Eosinophils
 - o Basophils
 - o Monocytes
 - o Lymphocytes
- Biochemistry
 - Total protein
 - o AST
 - o ALT
 - o Total bilirubin

ANOVA methods will be used to reveal a simultaneous influence of a group and time factors on the quantitative parameters.

The cross tables analysis will be used to reveal a correlation between the qualitative parameters (chi-squared test).

For the quantitative parameters, a comparison will be made by Student's t-test for the independent samples (in case of confirmation of hypothesis on normal variables distribution) or Mann–Whitney test (in case of rejection of hypothesis on normal

variables distribution); for the qualitative parameters—using Fisher's exact test.

To evaluate significance of the intragroup changes during the trial for repeatedly measured parameters, the paired Student's t-test (in case of confirmation of hypothesis on normal variables distribution) or paired Wilcoxon signed-rank test (in case of rejection of hypothesis on normal variables distribution) will be used; for the qualitative parameters McNemar's test will be used.

5 Presentation of statistical analysis results

5.1 Table templates

Table 1. Patient distribution

Patient distribution	Arm Number of patients (proportion, %)	Group Number of patients (proportion, %)
Included in the trial (screened)	n/N (%)	n/N (%)
Excluded at screening	n/N (%)	n/N (%)
Randomized	n/N (%)	n/N (%)
Discontinued prematurely	n/N (%)	n/N (%)
ITT population	n/N (%)	n/N (%)
PP population	n/N (%)	n/N (%)
Safety population	n/N (%)	n/N (%)

Table 2. Demographic and anthropometric patients' characteristics

Arm	Parameter	Age	Body weight	Height
	n			
	M			
	SD			
	95% CI			
	Min.			
	Max.			
	Me			
	IQR			
	n			
	M			
	SD			
	95% CI			
	Min.			
	Max.			
	Me			
	IQR			
	p			

Table 3. Patients distribution by sex

Arm	Men	Women
	n/N (%)	n/N (%)
	n/N (%)	n/N (%)
p		_

Table 4. Patients distribution by race

Race	Arm	Number of patients (proportion, %)	p
Caucasian		n/N (%)	
Caucasian		n/N (%)	
Negroid		n/N (%)	
Negroid		n/N (%)	
Asian		n/N (%)	
Asian		n/N (%)	
Unknown		n/N (%)	

	n/N (%)	
(Othors)	n/N (%)	
< Other >	n/N (%)	

Table 5. Social habits: alcohol abuse

	Arm	Number of patients (proportion, %)	p
Non-user		n/N (%)	
Non-user		n/N (%)	
Earman ugar		n/N (%)	
Former user		n/N (%)	
Command		n/N (%)	
Current user		n/N (%)	

Table 6. Social habits: smoking

	Arm	Number of patients (proportion, %)	p
Non-smoker		n/N (%)	
NOII-SHIOKCI		n/N (%)	
Former amelian		n/N (%)	
Former smoker		n/N (%)	
Current smoker		n/N (%)	
Current smoker		n/N (%)	

Table 7. The main vital signs (Visits 1, 2, 3)

Arm	Parameter	Systolic blood pressure	blood	Pulse rate	BR	Body temperature
	n					
	M					
	SD					
	95% CI					
	Min.					
	Max.					
	Me					
	IQR					
	n					
	M					
	SD					
	95% CI					
	Min.					
	Max.					
	Me					
	IQR					
	р					

Table 8. ECG results (Visits 1, 2, 3)

Arm	Parameter	ECG n/N (%)
	Reference	
	Deviation	
	Reference	
	Deviation	

Table 9. Hematology (Visits 1, 2, 3)

Arm	Parameter	Hemoglobin	RBC	ESR	WBC
	n				
	M				
	SD				
	95% CI				
	Min.				
	Max.				
	Me				
	IQR				
	n				
	M				
	SD				
	95% CI				
	Min.				
	Max.				
	Me				
	IQR				
	р				

Table 10. WBC differential (Visits 1, 2, 3)

Arm	Parameter	Neutrophils, total	Juvenile	Stab	Segmented	Eosinophils	Basophils	Monocytes	Lymphocytes
	n								
	M								
	SD								
	95% CI								
	Min.								
	Max.								
	Me								
	IQR								
	n								
	M								
	SD								
	95% CI								
	Min.								
	Max.								
	Me								
	IQR								
	р								

Table 11.Biochemistry (Visits 1, 2, 3)

Arm	Parameter	Total protein	ALT	AST	Total bilirubin
	n				
	M				
	SD				
	95% CI				
	Min.				
	Max.				
	Me				
	IQR				
	n				

M		
SD		
95% CI		
Min.		
Max.		
Me		
IQR		
р		

Table 12.A number of patients with normal and abnormal hematology parameters (Visits 1, 2, 3)

Arm	Parameter	Hemoglobin	RBC	ESR	WBC
	Reference				
	Deviation				
	Reference				
	Deviation				

Table 13.A number of patient with normal and abnormal WBC differential results (Visits 1, 2, 3)

Arm	Parameter	Neutrophils, total	Juvenile	Stab	Segmented	Eosinophils	Basophils	Monocytes	Lymphocytes
	Reference								
	Deviation								
	Reference								
	Deviation								

Table 14. A number of patient with normal and abnormal biochemistry parameters (Visits 1, 2, 3)

Arm	Parameter	Total protein	ALT	AST	Total bilirubin
	Reference				
	Deviation				
	Reference				
	Deviation				

Table 15. Concomitant diseases

Organ, system	Arm	Number of diseases (proportion, %)
		n/N (%)

Table 16. Concomitant therapy

Drug group	Arm	Number of prescriptions (proportion, %)
		n/N (%)

	n/N (%)
	n/N (%)
	n/N (%)
	n/N (%)

Table 17. Evaluation of throat pain severity according to VAS

Arm	Parameter	Visit 1	Visit 2	Visit 3
	n			
	M			
	SD			
	95% CI			
	Min.			
	Max.			
	Me			
	IQR			
	n			
	M			
	SD			
	95% CI			
	Min.			
	Max.			
	Me			
	IQR			
	p			

Table 18. TSS scores (Visits 1, 2, 3)

Arm	Amount of scores	Sore throat	Difficulty in swallowing	Salivation	Pharyngeal mucosa hyperemia	Fever
	0	n/N (%)	n/N (%)	n/N (%)	n/N (%)	n/N (%)
	1	n/N (%)	n/N (%)	n/N (%)	n/N (%)	n/N (%)
	2	n/N (%)	n/N (%)	n/N (%)	n/N (%)	n/N (%)
	3	n/N (%)	n/N (%)	n/N (%)	n/N (%)	n/N (%)
	0	n/N (%)	n/N (%)	n/N (%)	n/N (%)	n/N (%)
	1	n/N (%)	n/N (%)	n/N (%)	n/N (%)	n/N (%)
	2	n/N (%)	n/N (%)	n/N (%)	n/N (%)	n/N (%)
	3	n/N (%)	n/N (%)	n/N (%)	n/N (%)	n/N (%)
	p	n/N (%)	n/N (%)	n/N (%)	n/N (%)	n/N (%)

Table 19. Frequency of the recovery criteria achievement (total $TSS \le 2$) by Visits 2, 3

Arm	Parameter	Visit 2	Visit 3
	Criterion is met		
	Criterion is not met		
	Criterion is met		
	Criterion is not met		

Table 20. Global evaluation of treatment tolerability (Visits 2, 3)

Arm	Parameter	Tolerability evaluation by the patient	Tolerability evaluation by the physician
	n		
	M		

SD	
95% CI	
Min.	
Max.	
Me	
IQR	
n	
M	
SD	
95% CI	
Min.	
Max.	
Me	
IQR	
р	

Table 21. Registered adverse events occurred after initiation of the trial therapy

	Mile	d AEs	Moder	ate AEs	Seven	re AEs	To	otal	Total
Description	Serious	Non-serious	Serious	Non-serious	Serious	Non-serious	Serious	Non-serious	Serious +
	Scrious	1voii-scrious	Scrious	1 voii-scrious	Scrious	1 voii-serious	Scrious	14011-SCI IOUS	non-serious
				Organ sys	tem				
				Organ sys	tem				
_							•		

Table 22. Registered adverse events occurred after initiation of the reference therapy

	Milo	d AEs	Moder	ate AEs	Seve	re AEs	To	otal	Total
Description	Serious	Non-serious	Serious	Non-serious	Serious	Non-serious	Serious	Non-serious	Serious +
	Serious	Tion serious	5 6110 415	T (OII DOTTOUS	5411045	T (OII DUTTO GO	Serrous	1 (011 50110 45	non-serious
				Organ sys	tem				
	Organ system								

Table 23. AEs frequency by the nosological groups

Nosological group	Arm	Arm	p
Nosological group 1	n/N (%)	n/N (%)	
Nosology 1	n/N (%)	n/N (%)	
Nosology 2	n/N (%)	n/N (%)	
Nosology 3	n/N (%)	n/N (%)	
Nosological group 1	n/N (%)	n/N (%)	
Nosology 1	n/N (%)	n/N (%)	
Nosology 2	n/N (%)	n/N (%)	

Nosology 3	n/N (%)	n/N (%)	
Nosology 3	II/IN (/0)	11/1N (/0)	

Table 24. Compliance evaluation

Arm	Parameter	Compliance
	n	
	M	
	SD	
	95% CI	
	Min.	
	Max.	
	Me	
	IQR	
	n	
	M	
	SD	
	95% CI	
	Min.	
	Max.	
	Me	
	IQR	
	p	

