9.1.4 Safety parameters analysis

A descriptive part of the safety analysis will include an evaluation of incidences and two-sided CI 95% for the following parameters in every trial group:

- AEs: the incidence in total and for separate categories (according to MedDRA), for the trial and by groups;
- SAEs: the incidence in total and for separate categories (according to MedDRA), for the trial and by groups;
- Incidence of clinically significant changes of the physical examination results by visits and groups;
- Incidence of clinically significant changes of the laboratory results by visits and groups;
- Incidence of clinically significant changes of the vital signs (body temperature, BP, pulse rate, HR) by visits and groups;
- Incidence of clinically significant changes of the ECG parameters by visits and groups;
- Global tolerance evaluation during the trial by the Investigator and patient.

The Fisher's exact test will be used to compare incidences between the groups, and chi-square will be used to compare the global therapy tolerability by the Investigator and patient. The McNemar's test will be used to evaluate for the dynamic changes during the trial (before—after) for all the repeatedly evaluated incidences in every group.

In addition to the incidence, all the quantitative safety parameters will be presented in a table form (laboratory results, vital signs, ECG) by visits and groups. The difference will be evaluated using 2-way-ANOVA (group and visit numbers will serve as the relevant factors). The post-hoc criteria will be used in case of significant difference.

Safety analysis will be performed on the safety population.

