This trial has been designed and conducted to evaluate non-inferiority of the therapeutic efficacy and safety of the study drug Angal S, topical spray [menthol] containing 0.5 mg of lidocaine hydrochloride and 2 mg of chlorhexidine digluconate per ml (Sandoz d.d., Slovenia), when compared to ANTI-ANGIN® FORMULA, topical metered spray giving 0.12 mg of tetracaine hydrochloride and 0.24 mg of chlorhexidine bigluconate per dose (OOO Valeant, Russia) in the treatment of patients with uncomplicated acute infectious and inflammatory diseases of the pharynx accompanied by a sore throat. The objective of this Phase III trial is to demonstrate the non-inferior therapeutic efficacy of the study drug as compared to the reference product.

This Statistical Analysis Plan was developed in accordance with the following documents:

- Guidelines for examination of medicinal products, Vol. 1. Federal State Budgetary Institution Scientific Center for Expert Evaluation of Medicinal Products under the Ministry of Health of the Russian Federation (eds. A.N. Mironov). Moscow: Grif and K, 2013.
- ICH harmonized tripartite guideline. Statistical principles for clinical trials (E9). Current Step 4 version dated 5 February 1998.
- GCP rules of the Eurasian Economic Union (a draft).

The objective of this Statistical Analysis Plan is more detailed, compared to Section 9 of the trial protocol, description of the main principles of the protocol-based statistical analysis, description of the primary and secondary endpoints analysis methods, as well as other data obtained during the trial.

This Plan stipulates for consistence of the scheduled and conducted statistical analysis to the trial protocol, including definition of the analysis data sets, transformations and calculations for the endpoints, observations quantity needed, etc. No changes in this Statistical Analysis Plan compared to the trial protocol are envisaged.

2. Trial endpoints

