4.1.1 Descriptive statistics

Descriptive statistics for the initial data (obtained during Visit 1) for all randomized patients will be presented for the following variables:

- Age (a number of complete years as at Visit 1 date based on the date of birth);
- Sex, race;
- Social habits:
- Vital signs: initial systolic blood pressure, diastolic blood pressure, breathing rate, body temperature;
- Physical examination (presence/absence of deviations from the reference for organs and organ systems);
- Hematology, biochemistry;
- Electrocardiogram: presence/absence of deviations;
- Throat pain intensity according to VAS;
- TSS evaluation;
- Symptoms duration (calculated as a number of days as at Visit 1 date based on the first signs occurrence date);
- Time since the diagnostics to the therapy initiation (calculated as a number of days as at Visit 1 date based on clinical diagnostics date);
- Concomitant diseases: rate for the main organs and systems (MedDRA terms);
- Concomitant therapy: rate for the main drug groups;

Descriptive statistics for the data obtained by Visits 2 and 3 will be presented for the following variables:

- Vital signs: systolic blood pressure, diastolic blood pressure, breathing rate, body temperature;
- Physical examination (presence/absence of deviations from the reference for organs and organ systems);
- Throat pain intensity according to VAS;
- TSS evaluation;
- Evaluation of therapy efficacy;
- Hematology, biochemistry;
- 12-lead ECG:
- Global evaluation of treatment tolerability;
- Compliance evaluation;

All the AEs and SAEs registered during the trial will be classified according to MedDRA terms. A percentage of patients with the registered AEs with relevant codes (according to MedDRA terms and term groups) will be presented for every trial arm. In addition, AEs will be classified for severity and relationship with the study drug/comparator drug.

Descriptive statistics will be presented for all parameters for each group separately.

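### The SAP replaces the protocol's clinically significant safety changes with any deviation from the reference, and has no categorical output for vital signs

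*SAP*

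**What the plan says.** Protocol 9.1.4 lists the safety incidences to be reported with two-sided 95% confidence intervals. For the examination it names "Incidence of clinically significant changes of the physical examination results by visits and groups". The item for blood tests reads "Incidence of clinically significant changes of the laboratory results by visits and groups", and the one for the electrocardiogram reads "Incidence of clinically significant changes of the ECG parameters by visits and groups". Vital signs have a matching item. It then states: "The Fisher's exact test will be used to compare incidences between the groups".

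The SAP handles the same data differently.

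- **Laboratory.** Tables 12 to 14 in SAP 5.1 have two rows per arm, Reference and Deviation. Table 12 is titled "A number of patients with normal and abnormal hematology parameters (Visits 1, 2, 3".
- **ECG.** "Table 8. ECG results (Visits 1, 2, 3" has the same two rows.
- **Physical examination.** SAP 4.1.1 records "presence/absence of deviations from the reference for organs and organ systems", under descriptive statistics only.
- **Vital signs.** Table 7 gives continuous summaries. There is no categorical output.
- **Tests.** SAP 4.1.5 plans a between-group comparison of laboratory results and of the incidence of ECG changes, and names Fisher's exact test for qualitative parameters.

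The SAP introduction nevertheless says: "No changes in this Statistical Analysis Plan compared to the trial protocol are envisaged".

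**The concern.** A deviation from the reference need be neither a change nor clinically significant. A value outside the range at Visit 1 that is still outside it at Visit 2 counts as a deviation at both visits. So does a trivial excursion. The SAP therefore holds a different variable from the one the protocol specifies, without saying so, although Protocol 9.6 requires departures from the initial statistical plan to be described and justified.

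Safety is part of the trial objective (Protocol 3.1) and of the secondary goals (3.2). If the categorical test runs on any deviation, background excursions common to both arms enter the count and can hide a difference in the results that matter. The report would also lack a display the protocol promises, such as clinically significant ALT changes at Visit 2 by arm.

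**Working it through.** **1. Definitions side by side**

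| Domain | Protocol 9.1.4 | SAP | Test or p row in SAP |
|---|---|---|---|
| Laboratory | Clinically significant change | Reference / Deviation (Tables 12–14) | Fisher in 4.1.5; no p row |
| ECG | Clinically significant change | Reference / Deviation (Table 8) | Fisher in 4.1.5; no p row |
| Examination | Clinically significant change | Deviation present / absent (4.1.1) | None named |
| Vital signs | Clinically significant change | Continuous only (Table 7) | p row for the continuous values |

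The mismatch covers all four domains and needs no assumption. SAP 4.1.5 does not define the event for its Fisher test, but Reference and Deviation are the only categories the shells supply.

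**2. Where clinical significance survives in the SAP**

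Under SAP 3.6 the Investigator judges abnormal test results and registers adverse events. Protocol 8.3.4 makes clinically significant abnormal results adverse events, including those found at the last visit. SAP 4.1.4 compares adverse event incidence between arms by chi-squared, and Table 23 has a p column. Tables 21 to 23 group by organ system or nosology, not by parameter and visit.

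**3. How much the choice of event can matter**

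The documents give no figure to reproduce here: no background deviation rate, no expected safety rate and no power for a safety comparison. Inputs from the documents are 140 per arm (Protocol 9.2) and a two-sided test at 0.05 (SAP 3.10). All event rates below are assumptions. Power is the exact probability, summed over both binomial distributions, that Fisher's two-sided p is below 0.05.

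*6-point excess, kept intact on top of the background:*

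| Event counted | Rates | Power |
|---|---|---|
| Clinically significant only | 0.5% vs 6.5% | 74.6% |
| Any deviation, 5% background | 5% vs 11% | 37.4% |
| Any deviation, 10% background | 10% vs 16% | 26.3% |
| Any deviation, 20% background | 20% vs 26% | 18.4% |

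*Same case, with overlap.* If a patient with a background deviation can also have a significant one, the any-deviation rate is b + (1 − b)c, where b is the background rate and c the clinically significant rate. At b = 5% this gives 0.05 + 0.95 × 0.005 = 5.475% against 0.05 + 0.95 × 0.065 = 11.175%, and power is 32.8%. At b = 10% and 20% it is 21.4% and 12.9%.

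*2-point excess:* 0.5% vs 2.5% gives 7.8%. With backgrounds of 5%, 10% and 20% (5% vs 7%, 10% vs 12%, 20% vs 22%) it is 6.4%, 5.8% and 5.1%. There is almost nothing to lose.

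*Minor deviations also differ between arms:* take clinically significant rates of 2% vs 10% and minor deviations in 10% vs 20%. Any deviation is then 0.10 + 0.90 × 0.02 = 11.8% against 0.20 + 0.80 × 0.10 = 28%. Power is 91%, against 76.5% for clinically significant changes alone, so the loss reverses.

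**The case against.** Several points on the other side stand.

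- **The adverse event route.** Clinically significant results reach a between-arm comparison as adverse events. Tables 21 and 22 cover events after therapy began, so a stable Visit 1 abnormality should not enter. Laboratory tests and ECG are scheduled only at Visit 1 and once more, at Visit 2 or 3, so a split by visit adds modestly.
- **The shells look descriptive.** Tables 8 and 12 to 14 have no p row, while Tables 7 and 9 to 11 do. No test is named for examination findings, so no comparison there can lose power.
- **Other analyses.** McNemar's test within arms ignores patients who are abnormal at both visits. Laboratory values are also compared as continuous data, which does not depend on the dichotomy.
- **Limited background.** Protocol 5.2 bars leukocytosis, neutrocytosis, left shift, ESR above 30 mm/h and Hb below 120 g/l. This restrains some hematology deviations at baseline, though not those in biochemistry or ECG.
- **Descriptive framing.** Protocol 9.1.4 introduces the list as the descriptive part of the safety analysis.

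These points limit the consequence. They do not remove the mismatch: the protocol lists these incidences separately from adverse events and applies Fisher's test to incidences, and no SAP output delivers them.

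**Conclusion.** The inconsistency is established from the text: the SAP substitutes any deviation for clinically significant change, omits a categorical vital-signs output, and states that nothing differs from the protocol. It is a secondary safety matter, does not touch the primary endpoint, and should be corrected.

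The effect on power is conditional. With an assumed 6-point excess confined to clinically significant changes and equal background in both arms, power falls from 75% to between 37% and 18% for backgrounds of 5% to 20%. With a 2-point excess it is about 8% or less whichever event is counted, and where minor deviations differ too it can rise.

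A reader might infer that the safety comparison loses most of its power, or that a true difference would probably be missed. The documents do not support that: they give none of the rates needed, power no safety comparison, and send clinically significant results to the adverse event comparison. A reader might also infer that the protocol defines a change as a finding absent at Visit 1. It does not; that is a reasonable reading of the word, and the SAP should state it.

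**What to change.** In SAP 4.1.1, 4.1.5 and the table shells, add the incidence of clinically significant changes from Visit 1, by visit and arm, for laboratory results, ECG, vital signs and physical examination, with 95% CI and Fisher's exact test. State that a change means a finding not present at Visit 1, or worsened since then.

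Use the Investigator's judgement of significance described in SAP 3.6. The documents do not show a per-result significance field in the eCRF. If there is none, take the judgement from the adverse event record, linked to parameter and visit. SAP 3.6 speaks only of test results, so the SAP should name the source for vital signs and examination findings explicitly.

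Keep the Reference/Deviation tables, labelled as description only. If the sponsor prefers any-deviation counts for the comparison, the SAP should declare and justify that departure and drop the claim of no changes.

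The cost is SAP and shell wording, a few extra tables, and rarer events per parameter.

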5.2 List of figures

Figure 1. TSS scores changes by visits and trial arms

For the parameters listed below: pharyngalgia, difficulty in swallowing, salivation, hyperemia of pharyngeal mucosa, and body temperature increase, as well as for total sum of scores

Figure 2. Difference in proportions of patients who achieved efficacy criteria in every arm, 90% CI

Figure 3. Incidence of TSS scores decrease for 50% or more in the trial arms

Figure 4. A period of time required for disease signs resolution according to the patient's diary and the trial arms

Figure 5. Proportions of fully recovered patients by the trial arms

In Group A by Day 4 and in Group B by Day 5

Figure 6. Dynamic changes of pharyngalgia severity according to VAS by visits and trial arms

Figure 7. Dynamic changes of vital parameters by visits and trial arms

For the vital signs listed below: systolic blood pressure, diastolic blood pressure, pulse rate, breathing rate, body temperature.

Figure 8. Dynamic changes of hematology parameters by visits and trial arms

For the parameters listed below: Hb, RBC, ESR, WBC, neutrophils (juvenile, stab, segmented), eosinophils, basophils, monocytes, lymphocytes.

Figure 9. Dynamic changes of biochemistry parameters by visits and trial arms

For the parameters listed below: total protein, AST, ALT, total bilirubin.

6 List of approvals

Full name	Position	Signature	Date
		/Signature/
